### **2.7.2 Statistical hypothesis, model, and method of analysis**

No formal hypothesis testing will be conducted for secondary endpoints.

### **Patient preference of FCT, DT, and iron chelation at Week 28**

The proportion and percentage (%) of patients including 95% CI will be reported separately for preference and non-preference of FCT over DT, FCT over prior iron chelation, and DT over prior iron chelation at Week 28.

Homogeneity tests (including Cochran's Q test) will also be performed to check the homogeneity of the above three preferences. Exact and asymptotic p-values of Mc Nemar's test will also be presented as analogous to primary analysis, for pairwise treatment comparisons.

The OR of patient preference (i.e.  $OR=p_{12}/p_{21}$ ), 95% CI and p-values will also be presented for pairwise comparisons. For comparisons with iron-chelation, only patients who were pre-treated with iron chelation will be selected for pairwise comparisons.

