7.3.1 Preference Questionnaire

The preference questionnaire is a four item questionnaire. There are four separate versions depending on the week(s) that the questionnaire is administered.

For week 48 (primary endpoint) the first item asks the patients (or parents of young patients from 2 to 9 years old) which medicine they are currently taking with the response options: "Tablet to dissolve in liquid", "Film coated tablet ", "Sprinkle powder on food" and "I don't know". The second item asks which of the medicines did the patient "Like best" with the same response options as that of the first item. Finally, the third item asks the patient why he/she preferred the medicine they chose.

For week 28 the first item asks patients to choose from the following medicines: “Tablet to dissolve in liquid”, “Film coated tablet (taken once a day)”, “Tablet (taken 3 times a day)”, “Sprinkle powder on food”, “Injection” and “I don’t know”. The second items remain the same asking which medicine the patients like the best (out of the above response options). Similarly the third item remains the same.

For weeks 4 and 24 the first item asks patients to choose from the following medicines: “Tablet to dissolve in liquid”, “Tablet (taken 3 times a day)”, “Injection” and “I don’t know”. The second items remain the same asking which medicine the patients like the best (out of the above response options). Similarly the third item remains the same.

The following preference attributes are provided:

- Taste
- Aftertaste (taste left in your mouth after you swallow)
- Convenience (it’s not a problem to take your medicine - administration)
- Number of pills
- No/Less side effects
- Can correctly prepare the medicine
- Easier to remember to take the medicine
- Number of times you have to take the medicine
- No/Less pain on the injection site
- Gain my personal time with family and friends
- Other _____

The questionnaire is administered at week 4, week 24, week 28 and week 48. No total score is calculated on the preference questionnaire. Each item will be scored as the proportion of patients who select each response option.

7.3.2 mSICT – patients greater or equal to 10 years old

The Modified SICT (mSICT) questionnaire consists of 15 items that represent 3 domains; Adherence, Preference and Concerns.

The adherence domain consists of 7 items, 6 of which are measured using a 5 point response scale.

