Items 4, 5 and 6 use the response format 1 “Never”, 2 “Rarely”, 3 “Sometimes”, 4 “Most of the time”, 5 “Always”; Item 7 uses the response format 1 “Very easy”, 2 “Easy”, 3 “Neither easy nor hard”, 4 “Hard” and 5 “Very hard”; Items 8 and 9 use the response format 1 “Very bothered”, 2 “Quite bothered”, 3 “Moderately bothered”, 4 “A little bothered” and 5 “Not bothered at all”. An Adherence domain score will be calculated by summing these 6 items and as a result a higher score will indicate worse adherence.

Item 10 captures the reasons that the patient did not always take their medication as instructed and is only asked for patients who, at Item 6, indicated that they did not “Always” take their medication as instructed. These patients are instructed to choose all reasons that apply. Each response category will be coded as a binary item, for example taste will be an item with the

response format 0 “Not endorsed”, 1 “Endorsed”. For the “other” option, if there is a common response (>10%) it will be included as an additional binary response category in the analysis, otherwise other will be treated as Other 0 “Not endorsed”, 1 “Endorsed”. This item will be used as a standalone item to better understand the overall Adherence domain.

Satisfaction/preference domain consists of 3 items, 2 assess the patients’ satisfaction with the medication and are measured using a 5 point response scale with the response format: 1 “Very satisfied”, 2 “Satisfied”, 3 “Neither satisfied nor dissatisfied”, 4 “Dissatisfied”, 5 “Very dissatisfied”. A Satisfaction domain score will be calculated by summing these two items. Higher scores will indicate worse satisfaction.

The third item asks the patients to assess which medication for iron overload they prefer; this item will be used as a standalone item in the clinical trial.

Concerns domain consists of 3 items to address any concerns and worries the patient has with their medication. All 3 items are measured on a 5 point response scale with the response format 1 “Always”, 2 “Most of the time”, 3 “Sometimes”, 4 “Rarely” and 5 “Never”. A Concerns domain score will be calculated by summing these 3 items. Higher scores will indicate fewer concerns.

Two additional items (items 14 and 15) will also be scored as standalone items. Item 14 asks patients to choose attributes pertaining to why they chose to prefer a certain medication. Item 15 asks patients to “rank order” the medicines they have taken.

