10.5.2 Other secondary efficacy objectives

The following secondary analyses will be performed:

Patient preference of FCT, DT, and iron chelation at Week 28

Proportion and percentage, % (and 95% CI) of patients with preference and non-preference of FCT over DT, FCT over iron chelation, and DT over iron chelation will be summarized separately at Week 28.

Homogeneity test (Cochran's Q test) may be performed to check the homogeneity of the three preferences. Exact and asymptotic p-values of Mc Nemar's test will also be presented as analogous to primary analysis, for each pair of treatment comparison. For comparison of FCT

and DT with iron-chelation, only patients who are pre-treated with iron chelation will be selected.

Patient preference of DT and iron chelation at Week 4 and Week 24

Proportion and percentage, % (and 95% CI) of patients with preference and non-preference of DT over iron chelation will be summarized at Week 4 and Week 24. Exact and asymptotic p-values of Mc Nemar's test will also be presented as analogous to primary analysis. Only patients who are pre-treated with iron-chelation will be considered.

Reasons of patient preference

The reasons or factors influencing behind patient preference of FCT over DT will be summarized at Week 28 and 48. Proportions of patients for selecting each reason will be presented for each study treatment. Further summary of reasons behind non-preference of each study treatment will also be presented.

Compliance using pill count

Compliance is measured by pill /tablet count based on amount of medication dispensed, returned and reported as lost/wasted by the patient or caregiver. Compliance will be calculated for each treatment (FCT: Week 25- Week 48, DT: Baseline day 1 – Week 24) as the ratio of total count consumed to total count prescribed, where

total count consumed is derived from cumulative dispensed, returned and lost/wasted counts;

- total count prescribed is cumulative prescribed count

Analysis of covariance (ANCOVA) will be performed for comparison between both treatment groups (FCT and DT). The ANCOVA model for compliance endpoint will include treatment group and age group ((2 to <6 years, 6 to <10 years, 10 to <18 years, and ≥ 18 years) and thalassemia transfusion dependence (transfusion and non-transfusion dependent) as factors. Least squares estimates, 95% CI and p-value will be presented for each treatment and difference between treatments.

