14.3 Algorithm for Preference questionnaire completion

In case of treatment switch during the Core Phase of the study, the investigator must provide the preference questionnaire to the patient in the immediate next visit and then keep following the schedule of questionnaires pre-planned on [Table 7-1](#) and [Table 7-2](#).

Please see below the preference questionnaire version to be completed, based on treatment switch (yes/no) and when it occurred.

- Scenario 1 – Patient does NOT switch treatment

STUDY VISIT	QUESTIONNAIRE VERSION
Visit 4 (week 4)	Questionnaire vs. week 4 and 24
Visit 9 (week 24)	Questionnaire vs. week 4 and 24
Visit 10 (week 28)	Questionnaire vs. week 28
Visit 15 (week 48)	Questionnaire vs. week 48

- Scenario 2 – **Treatment switch** happens V3

STUDY VISIT	QUESTIONNAIRE VERSION
Visit 4 (week 4)	Questionnaire vs. week 28
Visit 9 (week 24)	Questionnaire vs. week 28
Visit 10 (week 28)	Questionnaire vs. week 28
Visit 15 (week 48)	Questionnaire vs. week 48

- Scenario 3 – Treatment switch happens between Visit 4 to Visit 7

STUDY VISIT	QUESTIONNAIRE VERSION
Visit 4 (week 4)	Questionnaire vs. week 4 and 24
Unplanned – next study visit after treatment switch	Questionnaire vs. week 28 eCRF: Summary page -
Visit 9 (week 24)	Questionnaire vs. week 28
Visit 10 (week 28)	Questionnaire vs. week 28
Visit 15 (week 48)	Questionnaire vs. week 48

- Scenario 4 – **Treatment switch** happens at **visit 8**

STUDY VISIT	QUESTIONNAIRE VERSION
Visit 4 (week 4)	Questionnaire vs. week 4 and 24
Visit 9 (week 24)	Questionnaire vs. week 28
Visit 10 (week 28)	Questionnaire vs. week 28
Visit 15 (week 48)	Questionnaire vs. week 48

- Scenario 5 – **Treatment switch** happens at **visit 9**

STUDY VISIT	QUESTIONNAIRE VERSION
Visit 4 (week 4)	Questionnaire vs. week 4 and 24
Visit 9 (week 24)	Questionnaire vs. week 4 and 24
Visit 10 (week 28)	Questionnaire vs. week 28
Visit 15 (week 48)	Questionnaire vs. week 48

- Scenario 6 – **Treatment switch** happens at visit 10 to 13

STUDY VISIT	QUESTIONNAIRE VERSION
Visit 4 (week 4)	Questionnaire vs. week 4 and 24
Visit 9 (week 24)	Questionnaire vs. week 4 and 24
Visit 10 (week 28)	Questionnaire vs. week 28
Unplanned – next study visit after treatment switch	Questionnaire vs. week 48 eCRF: Summary page -
Visit 15 (week 48)	Questionnaire vs. week 48

- Scenario 7 – **Treatment switch** happens at **visit 14**

STUDY VISIT	QUESTIONNAIRE VERSION
Visit 4 (week 4)	Questionnaire vs. week 4 and 24

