### **2.5.2 Statistical hypothesis, model, and method of analysis**

The null hypothesis is that there is no difference in the proportion of patients preferring FCT or DT at Week 48. The alternative hypothesis is that there is a difference in the proportion of patients preferring FCT or DT at Week 48.

Let  $p_{.1}$  denote the proportion of patients with preference (discordance) or no-preference (concordance) of DT and  $p_{1.}$  denote the proportion of patients with preference or no-preference of FCT, at Week 48.

In statistical terms, the following hypothesis will be tested for primary objective:

$H_1: p_{1.} = p_{.1}$ , versus  $H_{A1}: p_{1.} \neq p_{.1}$

This is equivalent to test:  $H_1: p_{12} = p_{21}$ , versus  $H_{A1}: p_{12} \neq p_{21}$ ,

where  $p_{12}$  and  $p_{21}$  denotes the proportion of patients with preference of FCT over DT and vice versa.

In other words,

$H_1$ : Deferasirox FCT is not different from deferasirox DT with respect to patient preference at Week 48

versus

$H_{A1}$ : Deferasirox FCT is different from deferasirox DT with respect to patient preference at Week 48

The primary analyses of testing patient preference of FCT over DT will be conducted via Mc Nemar's test. Both exact and asymptotic p-values will be presented for Mc Nemar's test for the matched pairs. Along with p-values, the estimates of proportions and percentages (%) of patient preferences and non-preferences for each study treatment will also be presented along with 95% CI (if required) using Clopper-Pearson method. The Type I error will be set to 2-sided  $\alpha=5\%$  or 1-sided  $\alpha=2.5\%$ . The testing will be done on the patients who have completed question 2 in the preference questionnaire.

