### **Preference questionnaire**

The preference questionnaire is a three item questionnaire. There are three separate versions depending on the week(s) that the questionnaire is administered. Week 4 and 24 contains preference questions on DT and iron chelators, Week 28 contain questions on all three medications and Week 48 on DT and FCT only.

Summaries of the preference questionnaires will be performed at Visits 4, 24, 28 and 48, if data is available, in Core phase of the study and additionally from the data collected at the time of immediate next visit based on patients who had treatment switching. No total score is calculated on the preference questionnaire. Each item will be scored as the proportion of patients who select each response option.

The analysis of preference data has been explained in [Section 2.5](#) and [Section 2.7](#).

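### Week 28 pairwise preferences are built from a single favourite choice, so they compare first-choice shares and can point the wrong way for DT versus previous chelation

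*SAP*

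**What the plan says.** Protocol 7.3.1 describes the Week 28 form. Its list holds the dispersible tablet, the film-coated tablet, a tablet taken three times a day, sprinkled powder, an injection and a don't-know option. Of item 2 it says: "The second items remain the same asking which medicine the patients like the best (out of the above response options". The SAP confirms the scope in 2.11: "Week 28 contain questions on all three medications". Both documents score each item only as the share of patients choosing each option.

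The analysis sections nevertheless ask for pairs. Protocol 10.5.2 has "patients with preference and non-preference of FCT over DT, FCT over iron chelation, and DT over iron chelation will be summarized separately", and SAP 2.7.2 has results "separately for preference and non-preference of FCT over DT, FCT over prior iron chelation, and DT over prior iron chelation at Week 28", each with a 95% CI. Exact and asymptotic McNemar p-values "will also be presented as analogous to primary analysis, for pairwise treatment comparisons", together with OR = p12/p21. Comparisons with earlier chelation are restricted to pre-treated patients. SAP 2.7.2 does not name the questionnaire item. For the primary analysis, SAP 2.5.2 does: "The testing will be done on the patients who have completed question 2 in the preference questionnaire".

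Two other places matter. Under mSICT, for patients aged 10 or over, Protocol 7.3.2 says: "Item 15 asks patients to “rank order” the medicines they have taken". That item is summarised on its own and is not linked to the preference endpoints. Appendix 14.3 sets which form is used: "Please see below the preference questionnaire version to be completed, based on treatment switch (yes/no) and when it occurred".

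**The concern.** One favourite does not order the two medicines that were not chosen. For DT versus previous chelation, every patient whose favourite is FCT is silent, and FCT is the formulation the trial expects most patients to choose. Neither document says how a favourite outside the pair is classified. On any reading by analogy with the primary analysis, such a patient adds nothing to p12 or p21.

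The report would then carry an odds ratio, a CI and p-values under a pairwise label, while the quantity estimated is the ratio of the two medicines' first-choice shares. A reader would take it as how patients rate DT against the chelator they left. FCT-first patients may hold a different view on that from the rest.

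The other two pairs have the same weakness, through patients who favour previous chelation (FCT versus DT) or DT (FCT versus previous). The Week 4 and 24 endpoint for DT versus previous chelation is also touched, for early switchers who are given the form that lists FCT.

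**Working it through.** **Plan's own figure.** None is given for Week 28. The only sample-size figure is for Week 48: (1.960 + 0.842)² × (0.70 − 0.20²) / 0.20² = 7.849 × 0.66 / 0.04 = 129.5, so 130; and 130 / 0.90 = 144.4, so 145. It reproduces, and nothing below depends on it.

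**Inputs.**
- F, D, P: first-choice shares for FCT, DT and previous chelation among pre-treated patients. The documents give no Week 28 values, so these are assumed. Don't-know and other answers are set to zero.
- For scale: the Amendment 1 rationale in the protocol cites 41–60% preferring FCT in an earlier study. The Week 48 planning values are FCT 45%, DT 25% and no preference 30%. Assigning that last 30% to previous chelation is an assumption made here.
- f: the share of FCT-first patients who like DT more than their previous chelator. Assumed.

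**Formulas.**
- OR under the plan: D / P.
- True pairwise OR: (D + fF) / (P + (1 − f)F).
- Possible share liking DT more than previous chelation: from D (f = 0) to D + F (f = 1).
- When D < P, the direction reverses if D + fF > P + (1 − f)F, that is f > (P − D + F) / (2F).

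**Results for DT versus previous chelation.**

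| F/D/P (%) | OR under plan | Possible DT share | Reverses if f exceeds | True split at f = 0.8 |
|---|---|---|---|---|
| 45/25/30 | 0.83 | 25–70% | 0.50/0.90 = 0.56 | 61 v 39, OR 1.56 |
| 60/15/25 | 0.60 | 15–75% | 0.70/1.20 = 0.58 | 63 v 37, OR 1.70 |
| 60/10/30 | 0.33 | 10–70% | 0.80/1.20 = 0.67 | 58 v 42, OR 1.38 |

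In the last row, with an assumed 100 pre-treated patients, the plan would show 10 v 30, exact p = 0.002 in favour of previous chelation. The true split at f = 0.8 would be 58 v 42 in favour of DT (p = 0.13).

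**When the direction is right.** At 45/25/30 and f = 0.5 the true split is 47.5 v 52.5 (OR 0.90), the same direction as the plan. If FCT-first patients divide as the others do, f = D/(D + P) = 25/55 = 0.45. The true DT share is then 0.25 + 0.4545 × 0.45 = 45%, again the same direction.

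**FCT versus DT at 45/25/30.** Here the 30% who favour previous chelation are silent. Reversal would need more than (0.45 − 0.25 + 0.30) / (2 × 0.30) = 83% of them to like DT more than FCT, so this pair is much less exposed.

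**Homogeneity test.** With one choice per patient the three indicators in SAP 5.4.2 are mutually exclusive, and Cochran's Q reduces to the chi-square for equal first-choice shares. For first choices of 55, 20 and 25, Q = 2 × [3 × (55² + 20² + 25²) − 100²] / (300 − 100) = 21.5. The chi-square is (21.67² + 13.33² + 8.33²) / 33.33 = 21.5.

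**Weeks 4 and 24.** The standard form for these visits lists DT and previous chelators without FCT. Appendix 14.3 gives the Week 28 form instead at Weeks 4 and 24 in Scenario 2, and at Week 24 in Scenarios 3 and 4. The SAP analysis for these weeks does not separate those patients.

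**The case against.** The case against has real weight.

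- **The item is inferred.** SAP 2.7.2 does not say that question 2 is used at Week 28, nor how a favourite outside the pair is handled. This stands as a limit. The inference is still strong, because the analysis is declared analogous to the primary one and item 2 is the form's only like-best question.
- **The stated endpoint is met.** The Week 28 endpoint is the proportion preferring each of FCT, DT and previous chelation, and first-choice shares answer that. This stands too, and is why item 2 should remain. It does not support the pairwise labels, ORs and p-values.
- **DT versus previous chelation is asked directly at Weeks 4 and 24.** That is true except for early switchers, whose number is unknown. No comparison between those weeks and Week 28 is planned, so a lack of comparability is not itself a fault.
- **Little rests on it.** SAP 2.7.2 plans no formal testing of secondary endpoints. This limits the weight of the point, but the intervals, ORs and p-values will still be presented.

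Two stronger readings are tempting. A reader might infer that the Week 28 result will have the wrong direction. The documents give neither first-choice shares nor rankings at Week 28, and with f at or below 0.5 the examples above do not reverse. A reader might also infer that mSICT item 15 orders every pair for every patient and should replace item 2. The protocol says only that patients rank the medicines they have taken. It gives no rule for ties, incomplete ranks or patients with two previous chelators, and the observer form for ages 2 to 9 omits the item. Replacement would also change the instrument and population of an endpoint defined by the preference questionnaire.

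**Conclusion.** The point holds. As written, the Week 28 analysis presents a comparison of first-choice shares as pairwise preference. FCT-first patients carry no information on DT versus previous chelation, and would be about half of those analysed if the cited 41–60% applied to pre-treated patients here.

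The size of the error is conditional. At 45/25/30% the plan's OR of 0.83 is compatible with a true DT share anywhere from 25% to 70%, and the direction changes only if f exceeds about 0.56. In the other two examples the threshold is 0.58 and 0.67. All of this rests on assumed shares, an assumed f, and item 2 being the source. The mislabelling does not depend on those shares or on f. For a secondary endpoint without formal testing, it should be corrected but does not threaten the primary result.

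**What to change.** 1. In SAP 2.7.2, keep item 2 as the Week 28 endpoint, but report and label it as first-choice shares. Drop the three pairwise labels for it.
2. Add a supplementary pairwise analysis at Week 28 from the mSICT item 15 ranks, in pre-treated patients aged 10 or over who ranked both medicines of the pair. State the rule for ties, incomplete ranks and patients with two previous chelators.
3. In the Week 4 and 24 analysis, show separately the patients who were given the Week 28 form.

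The cost is SAP wording and one derivation from data already collected. The supplementary estimate leaves out ages 2 to 9, for whom only first-choice shares are available. It must be labelled post hoc if added after the Week 48 (interim) database lock; the SAP's document history already carries an entry dated April 2021 made after that lock.

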### **2.7.1 Secondary endpoints**

All the secondary efficacy evaluation will be performed on FAS population.

Refer to [Table 1.2.1](#) of Section 1 for the list of secondary endpoints.

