### 3 Sample size calculation

Based on data from the ECLIPSE study (Taher et al 2018), the following assumptions have been made at Week 48, the patient preference for deferasirox FCT (formulation) is 45% and preference for deferasirox DT (formulation) is 25% and no preference to either of the formulations is 30%. This means the discordant pairs is 70 % (i.e. 70% preferred one formulation over another, 45 %) and concordant pairs= 30% (assuming same preference for each formulation, 15%).

At least 130 patients are needed at Week 48 to have 80% power to detect the difference of patient preference of 20% (i.e. 45% preference of FCT over DT and 25% preference of DT over FCT) at a two sided significance level of 0.05 using McNemar's test for matched pairs.

To allow for roughly 10% of subjects with missing measurement, a total of approximately 145 evaluable patients aged  $\geq 2$  years male or female with TDT or NTDT requiring chelation therapy due to iron overload, need to be enrolled. Patients may have been previously treated with iron chelators (other than deferasirox DT) or be chelation-naïve.

EAST 6.0 is used to calculate the sample size.

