## 5.4.2 Secondary analysis

### SAS code for Homogeneity test:

```
proc freq data=;  
tables Drug_A Drug_B Drug_C / nocum;  
tables Drug_A*Drug_B*Drug_C / agree noprint;  
format Drug_A Drug_B Drug_C $ResponseFmt. ;  
weight Count;  
title 'xxxxxxx';  
run; Drug_A=FCT, Drug_B= DT and Drug_C= iron chelation
```

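### The SAP does not restrict Cochran's Q at Week 28 to pre-treated patients, so chelation-naïve patients enter by default and bias a descriptive test

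*SAP*

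**What the plan says.** - **The test.** SAP 2.7.2, on Week 28 preference: "Homogeneity tests (including Cochran's Q test) will also be performed to check the homogeneity of the above three preferences". The sentence names no population. Protocol 10.5.2 had made the test optional: "Homogeneity test (Cochran's Q test) may be performed to check the homogeneity of the three preferences".
- **Default population.** SAP 2.7.1: "All the secondary efficacy evaluation will be performed on FAS population". The FAS requires one dose of each formulation and takes no account of prior chelation.
- **Who is in it.** SAP section 3: "Patients may have been previously treated with iron chelators (other than deferasirox DT) or be chelation-naïve". Neither document gives the expected naïve share.
- **The restriction.** SAP 2.7.2: "For comparisons with iron-chelation, only patients who were pre-treated with iron chelation will be selected for pairwise comparisons". The protocol's counterpart, placed after the sentences on Q and on McNemar's test, says that for comparing FCT and DT with iron chelation "only patients who are pre-treated with iron chelation will be" selected. It has no limit to pairwise tests and does not name Q.
- **The neighbouring analysis.** For Weeks 4 and 24, SAP 2.7.2 admits only pre-treated patients, without any such limit.
- **The code.** SAP 5.4.2 gives "tables Drug_A*Drug_B*Drug_C / agree noprint" with no subset statement.
- **Status.** SAP 2.7.2 says that secondary endpoints have no formal hypothesis tests.

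**The concern.** Cochran's Q asks whether the three options are chosen equally often. A patient who never took a prior chelator has only FCT and DT to compare, so that patient's zero for prior chelation reflects treatment history, not preference. Pooled with pre-treated patients, such zeros lower the prior-chelation share and raise the other two. A small p-value could then be read as patients favouring deferasirox over their earlier chelator when it partly reflects how many naïve patients were enrolled. If pre-treated patients in fact favour their earlier chelator, the same zeros push the shares back towards equality and can hide it. In either case the omnibus result would rest on a different population from the pairwise results against prior chelation printed beside it.

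**Working it through.** **Plan's own figure.** The documents give no operating characteristics for Q. The one planning number used here is N = 130 for the primary McNemar test (45% vs 25%, two-sided 0.05, 80% power). It reproduces with the variance under the alternative:

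N = (1.960 + 0.842)² × (0.70 − 0.20²) / 0.20² = 129.5, so 130. Allowing 10% missing: 130 / 0.90 = 144.4, so 145.

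N = 130 is a Week 48 figure, borrowed here as a plausible Week 28 count.

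**Step 1: form of Q.** The like-best item is treated as a single choice, so each patient scores 1 on at most one of the three indicators. With counts C₁, C₂, C₃ and n = ΣC, Cochran's Q reduces to

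Q = 3ΣC²/n − n,

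the chi-square goodness-of-fit statistic for three equal shares (2 df, 5% critical value 5.99). Patients choosing none of the three drop out.

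**Step 2: effect of naïve patients.** Let f be the naïve share (assumed). Suppose pre-treated patients choose each option one third of the time, and naïve patients split evenly between FCT and DT and are coded 0 for prior chelation. Then:

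- FCT share = DT share = (1 − f)/3 + f/2 = 1/3 + f/6
- prior-chelation share = 1/3 − f/3
- non-centrality = 3N(f²/36 + f²/36 + f²/9) = N f²/2

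At f = 0.20 and N = 130 this is 130 × 0.04/2 = 2.6, for which the non-central chi-square gives 28.3% rejection.

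**Step 3: simulation.** 40,000 trials per cell, N = 130, pre-treated patients truly homogeneous. The columns give false rejection by unrestricted Q under three assumptions about patients who choose none of the three.

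| Naïve share (assumed) | None in either group | 10% of pre-treated, no naïve | 30% in both groups |
|---|---|---|---|
| 5% | 5.8% | 5.9% | 5.8% |
| 10% | 9.6% | 10% | 8.1% |
| 20% | 27.5% | 30% | 20.0% |
| 30% | 59.9% | 64% | 43.2% |
| 40% | 89.2% | 92% | 72.3% |

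At a 50% naïve share the first and third columns reach 99.2% and 92.8%.

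**Step 4: after the fix.** With Q restricted to pre-treated patients, rejection is 4.6% to 5.2% at every naïve share tried, so the nominal level is restored.

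**Step 5: the opposite error.** Let pre-treated patients choose FCT, DT and prior chelation 25/25/50. At f = 1/3 the pooled shares are 0.25 × 2/3 + 0.5 × 1/3 = 1/3 for each formulation and 0.50 × 2/3 = 1/3 for prior chelation, so the real difference cancels exactly. By simulation at f = 0.30, rejection falls from 83.9% (pre-treated only) to 4.4% (everyone).

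**The case against.** **The intent may already be right.** The protocol's restriction is not limited to pairwise tests, the SAP says its analysis sets follow the protocol unless otherwise specified, and SAP section 4 lists no changes. Q could therefore be read as covered. This shows that the fix agrees with the protocol. It does not settle the SAP, whose own sentence ends with the words for pairwise comparisons and whose default is the FAS.

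**The code proves little.** That stands. It is a template with an empty dataset name, and the McNemar template has no subset either, although the text restricts those comparisons. The point rests on the text of 2.7.1 and 2.7.2.

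**The zeros are not enforced.** That also stands. The Week 28 form described in protocol 7.3.1 offers the three-times-daily tablet and the injection to everyone, and SAP 2.3.3 defines naïve by the last 6 months, so some naïve patients may have used a chelator earlier. Zeros are expected for most of them, not guaranteed. Nor does the SAP say whether the value is coded 0 or missing; if missing, the three-way table would ordinarily omit these patients and the bias would not arise. Leaving that to programming is itself a reason to name the population.

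**Little hangs on Q.** It is descriptive and has no direction, the pairwise tests and odds ratios against prior chelation are already restricted, and results are also to be shown by chelation status where applicable. This limits the importance of the point but does not make the overall Q valid.

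**A stronger reading to avoid.** A reader might infer that the test must reject homogeneity by construction. The documents do not support that. They give no naïve share, the inflation is under one percentage point at a 5% share, rejection becomes near-certain only at shares of about 40–50%, and the bias can also suppress rejection.

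**Conclusion.** The point holds as a minor correction. As the SAP is worded, Q at Week 28 takes in chelation-naïve patients, and its type I error then depends on how many there are: roughly nominal at a 5% share, 8–10% at 10%, 20–30% at 20% and 43–64% at 30%. These figures assume N = 130, 0/1 coding with 0 for naïve patients, an even FCT/DT split among them, and equal preferences among the pre-treated. The naïve share is unknown, so the size in this trial cannot be fixed from the documents. The bias runs in both directions. The primary Week 48 analysis, its sample size and the pairwise comparisons with prior chelation are untouched.

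**What to change.** In SAP 2.7.2, state that Cochran's Q at Week 28 is computed only in FAS patients pre-treated with iron chelation (as classified in 2.3.3) who answered the Week 28 like-best item. Add the matching subset condition to the homogeneity code in 5.4.2. Report FCT against DT in naïve patients separately, which the planned presentation by chelation status largely covers.

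The cost is one sentence and one line of code, with no new data. The test uses fewer patients and so loses some power: in the 25/25/50 example, the restricted test rejects in 83.9% of trials at a 30% naïve share, against 94.8% if all 130 were pre-treated.
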